## 2.0 LIST OF ABBREVIATIONS

AE	Adverse Event
CCC	Clinical Coordinating Center
CFR	Code of Federal Regulations
COVID-19	Coronavirus Disease of 2019
CRF	Case Report Form
CTCAE	Common Terminology Criteria for Adverse Events
CTMS	Clinical Trial Management Software
DHHS	Department of Health and Human Services
DMC	Data Monitoring Committee
DSMP	Data & Safety Monitoring Plan
eCRF	Electronic Case Report Forms
EDC	Electronic Data Capture
EHR	Electronic Health Record
FDA	Food and Drug Administration
GCP	Good Clinical Practice
HIPAA	Health Insurance Portability and Accountability Act
ICTR	Institute for Clinical and Translational Research
IRB	Institutional Review Board
NP	Nasal Pharyngeal
OHRP	Office for Human Research Protections
OnCore	Online Collaborative Research Environment
PCR	Polymerase Chain Reaction
PHI	Protected Health Information
PI	Principal Investigator
POC	Point of Contact
REDCap	Research Electronic Data Capture
SAE	Serious Adverse Event
SAP	Statistical Analysis Plan
UP	Unanticipated Problem

## 3.0 STUDY SUMMARY

### 3.1 Synopsis

Full Title	The utility of "lollipop" oral swabs in the diagnosis of COVID-19 in an inpatient setting
Short Title	Inpatient COVID-19 Lollipop Study
Protocol Number	2023-0290
ClinicalTrials.gov Identifier & Summary	NCT ID pending. This study is being done to see if collecting saliva samples with a "lollipop" collection method works as well as nasal samples for COVID-19 PCR testing.

Number of Site(s)	UW-Madison will be the only site enrolling subjects.
Main Inclusion Criteria	
 
• Individuals at least 4 years of age
 
• Admitted to a hospital
 
• Verified COVID-19 according to positive NP PCR test criteria
 
• Enroll within 47 hours of the diagnostic NP swab; lollipop swab collected within 48 hours of the diagnostic NP swab
 

Main Exclusion Criteria	
 
• Unable to suck on a swab
 
• Previous participation in this study
 
• Require translation services for medical care
 

Objective(s)	
Primary Objective
 
 
• To determine the performance characteristics of oral lollipop swabs compared to NP swabs for diagnosing COVID-19 via PCR molecular testing.
 
 
Secondary Objectives
 
 
• To identify clinical characteristics of patients when there are discordant results for NP and oral lollipop test results.
 

Endpoints	
Primary Endpoint
 
 
• Tabulated results from NP vs. lollipop swab-based PCR COVID-19 tests.
 
 
Secondary Endpoints
 
 
• Correlation of clinical characteristics to participants with discordant test results
 

Study Design	This is a prospective quantitative study evaluating the utility of a novel method of saliva collection for COVID-19 testing.
FDA Regulatory Overview	
-
 
The investigational swab and associated COVID-19 PCR test are FDA regulated and involve an IDE-exempt in vitro diagnostic device.

Study Device	The lollipop collection swab and the lollipop swab processing procedure are both investigational.
Total Number of Subjects	Up to 225 subjects will be enrolled.
Study Population	COVID-positive patients ages 4 and above admitted to a hospital in the Madison, Wisconsin metropolitan area.
Statistical Methodology	The results of the lollipop swab will be compared to that of the known positive NP PCR to estimate the performance of the lollipop test to diagnose COVID-19. Falsely negative lollipop samples will be compared with the corresponding NP sample for cycle threshold.
Estimated Subject Duration	The duration of the study for each subject is a single study visit that will take approximately 30 minutes.
Estimated Enrollment Period & Study Duration	Study enrollment will occur over 6 months with the total expected duration of the trial to be 12 months.

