## 5.4 Rationale

It has been reported that the ACE2 receptor is a main host cell receptor for SARS-CoV-2 and plays a crucial role in the viral entry into human cells. There is high expression of the ACE2 receptor in epithelial cells of the oral mucosa and tongue. PCR of saliva samples have been shown to be an alternative to NP swabs.

NP swabs are cumbersome to perform, uncomfortable for the patient, require assistance from health care providers, and are not practical for large daycare and school-aged groups that may warrant repeated testing. Salivary samples can be challenging due to volume of saliva required to run the test. An oral swab, sucked on like a lollipop is a less invasive, quicker, and an easier sample to perform that may also be obtained by the individual or parent at home without a medical provider. Therefore, oral lollipop swabs may facilitate testing in adults, younger children, greater numbers of children, and when multiple longitudinal samples may be required. The oral lollipop swab will be a much more comfortable sample to obtain and will allow for the repeated and large-scale testing of populations.

In addition, PCR is a very sensitive technique that can identify persistent viral nucleic acid following acute infection. For this reason, repeat PCR tests are not recommended to determine the end point of COVID-19 isolation. Moreover, repeat COVID-19 screening via PCR is not recommended within 90 days of past infection. These persistently positive NP PCRs can lead to diagnostic and infection prevention challenges as distinguishing which tests represent true, acute, and transmissible infection versus past, non-viable, and non-transmissible virus is frequently not possible.

If the oral lollipop swab has a similar performance to the NP swab, then a new testing option, ideal for frequent testing of large cohorts of patients, especially young children, will be possible. In addition, identifying differences between NP and oral lollipop swab positivity could determine whether oral lollipop swabs have less risk of persistent, post-infectious, positivity.

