## 6.0 STUDY OBJECTIVES AND ENDPOINTS

Objectives	Endpoints
Primary To determine the performance characteristics of oral lollipop swabs compared to NP swabs for diagnosing COVID-19 via PCR molecular testing.	Tabulated results from NP vs. lollipop swab-based PCR COVID-19 tests.
Secondary To identify clinical characteristics of patients when there are discordant results for NP and oral lollipop test results.	Correlation of clinical characteristics to participants with discordant test results

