## 7.0 STUDY DESIGN

### 7.1 General Design

The Inpatient COVID-19 Lollipop Study is a prospective, single-center study to determine if oral lollipop swabs provide an adequate/optimum sample for diagnosing COVID-19. A total of up to 225 COVID-positive inpatients ages 4 years and older will be enrolled at one study sites. Subject accrual will occur over 6 months with the total duration of the study expected to be 12 months.

Eligible subjects will complete 1 visit that will last approximately 30 minutes. After the study team obtains informed consent and assent, if applicable, the study team will provide verbal instructions and supervise participants as they suck on a flocked swab for 20 seconds. The sample will be labeled with the study ID code and date of sample acquisition, and the result (positive or negative) of the lollipop swab will be compared to the NP swab results in the participant's medical record. Clinical information including symptoms, duration of symptoms, known past COVID-19 infections, known COVID-19 household contacts within 90 days, and COVID-19 immunization status will be assessed via conversation with the participant and review of the electronic medical record. Laboratory information including the cycle threshold of the NP sample will be collected. Each participant will be classified as having either symptomatic or asymptomatic infection. The electronic medical record will be reviewed for medical record number, birthdate, and the above clinical information regarding COVID-19. The sample will be sent to the Wisconsin Veterinary Diagnostic Lab (WVDL) for performance of the PCR for SARS-CoV-2. The specimens will be discarded in the lab after the sample has been processed.

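### The one stated cycle-threshold analysis uses only lollipop-negative participants, so it cannot show whether discordance is related to NP Ct; adding a lollipop-positive comparator is a cheap improvement

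*Combined protocol and SAP*

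**What the plan says.** Ct appears in two places in the combined protocol and SAP.

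- Section 3.1, Statistical Methodology: "Falsely negative lollipop samples will be compared with the corresponding NP sample for cycle threshold".
- Section 7.1: "Laboratory information including the cycle threshold of the NP sample will be collected". This is not restricted to discordant participants.

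Section 7.1 treats the lollipop outcome as binary: "the result (positive or negative) of the lollipop swab will be compared to the NP swab results". It mentions no lollipop Ct.

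The secondary objective is "To identify clinical characteristics of patients when there are discordant results for NP and oral lollipop test results", and its endpoint in section 6.0 is "Correlation of clinical characteristics to participants with discordant test results". Neither names Ct, a comparison group or a method. Section 7.1 introduces the clinical variables separately ("Clinical information including symptoms, duration of symptoms, known past COVID-19 infections") from the laboratory information that contains Ct.

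Section 12.1 has hypotheses by symptom duration and for asymptomatic participants. Section 12.4 plans sensitivity and specificity, overall and by symptom subgroup. Neither mentions Ct.

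**The concern.** Everyone enrolled has a positive NP PCR (section 8.1, inclusion criterion 5). Discordant therefore means lollipop-negative, and concordant means lollipop-positive. The synopsis sentence uses only the first group. To say that lollipop-negative results occur mainly at high NP Ct, one must know the NP Ct of the lollipop-positive participants, and the sentence leaves them out.

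What is at stake is one supportive result. The team could report a median NP Ct for the false negatives and have no planned yardstick for calling it high. A comparator chosen after the results are seen would be post hoc.

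**Working it through.** **1. What the stated analysis can estimate.** Let F be the distribution of NP Ct in lollipop-negative participants and G the distribution in lollipop-positive participants. A relation between discordance and NP Ct means that F differs from G. The stated analysis gives information on F only, and any summary of F is unchanged whether G lies below, on or above it. If a lollipop Ct did exist for the false negatives, a paired NP-minus-lollipop difference would still be computed inside the lollipop-negative group and would still say nothing about G.

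**2. The plan's own figure.** The plan gives no figure for the Ct analysis. Its sample size of 206 (section 12.2: 88% in the pilot, 80% anticipated, 5% Type I error, 90% power) reproduces as a two-sided one-sample test of a proportion:

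n = (1.960·√(0.88·0.12) + 1.282·√(0.80·0.20))² / (0.88 − 0.80)² = 206.5.

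This does not depend on Ct.

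**3. Group sizes for the missing contrast**, with 206 evaluable participants:

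- 80% sensitivity: 206 × 0.20 ≈ 41 lollipop-negative, 165 lollipop-positive.
- 88% sensitivity: 206 × 0.12 ≈ 25 lollipop-negative, 181 lollipop-positive.

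**4. Precision of the contrast.** The documents give no SD for Ct, so the results are in SD units. The standard error of a difference in means is √(1/n₁ + 1/n₂), and the 95% half-width is 1.960 times that. The detectable difference at two-sided 5% is 2.802 times the standard error for 80% power and 3.242 times for 90% power.

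| Groups | SE (SD units) | 95% half-width | Detectable, 80% power | Detectable, 90% power |
|---|---|---|---|---|
| 41 vs 165 | 0.174 | 0.34 | 0.49 | 0.57 |
| 25 vs 181 | 0.213 | 0.42 | 0.60 | 0.69 |

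**5. The same in rank terms**, which need no SD. Let P be the probability that a lollipop-negative participant has a higher NP Ct than a lollipop-positive one (0.50 means no relation). By Noether's formula at 80% power, P = 0.5 + √(7.849 / (12·c·(1 − c)·N)), where c is the lollipop-negative fraction.

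- c = 41/206 = 0.199, N = 206: P = 0.64.
- c = 25/206 = 0.121, N = 206: P = 0.67.

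**6. Missing NP Ct.** The documents do not say how often NP Ct is available. If 20% had none (an assumption), N falls to 165. The detectable P becomes 0.66 (33 vs 132) or 0.69 (20 vs 145).

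Steps 3 to 6 show that the added comparison is feasible with modest precision. They do not measure an error in the plan.

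**The case against.** **The secondary endpoint already covers this.** Correlating characteristics with discordance needs variation in discordance, so a concordant group is implied, and NP Ct is collected for everyone. Section 7.1 later refers back to the clinical information above, which could be read to include Ct. This partly stands: the endpoint is loose enough to take in the comparison. But it names neither Ct nor a comparator, and the one sentence that does address Ct names only false negatives.

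**The data list is not exhaustive.** Section 10.3.1 refers to a Data Collection Sheet that is not among the documents, and the list in section 7.1 is introduced as inclusive. This stands. A reader might infer that no lollipop Ct will exist; the documents do not establish that. Step 1 of the working does not depend on it.

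**Ct is peripheral.** It is in no objective, endpoint or hypothesis, and the symptom-duration and asymptomatic analyses do not rely on it. This stands, and it limits the weight of the point.

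**The link to persistent positivity.** A reader might infer that the gap undermines the aim in section 5.4, where "identifying differences between NP and oral lollipop swab positivity could determine whether oral lollipop swabs have less risk of persistent, post-infectious, positivity". The documents do not support that. Section 5.4 does not mention Ct, and nothing in the plan says what a high Ct means for past or non-viable infection. Any such link is an assumption.

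**Conclusion.** The point holds as a cheap improvement to a supportive analysis. The only Ct analysis stated describes lollipop-negative participants, and on that alone the study cannot say whether discordance is related to NP Ct. The comparison that could is not specified, although the data listed for collection allow it.

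The size of the contrast rests on 206 evaluable participants, sensitivity between 80% and 88%, and NP Ct recorded for all. On those assumptions a 95% interval for a mean difference has a half-width of about 0.34 to 0.42 SD. It would be wider if NP Ct is often missing or discordant results are fewer.

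It would go too far to read this as a flaw in the main result. The primary sensitivity estimate and the sample size of 206 do not use Ct and are unaffected.

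**What to change.** Keep the synopsis sentence as description. Add to it, and to section 12.4:

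*NP cycle threshold will be compared between lollipop-negative and lollipop-positive participants (median and IQR by group; difference with 95% CI); the number without a recorded NP Ct will be reported.*

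This is a two-group description, so it fits the statement in section 12.6 that no formal multivariate or longitudinal modelling is involved. It should be labelled supportive.

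The cost is a little extra analysis. It needs no new data, visits or participants, because NP Ct is already listed for collection. The drawback is modest precision, so the interval should be reported and a wide one not read as evidence of no relation.

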### 3.2 Schematic of Study Design

Prior to Enrollment

Screen potential participants by inclusion and exclusion criteria. Conduct consenting process and obtain informed consent.

Visit 1  
Time Point

Confirm and document eligibility. Administer verbal questionnaire to collect clinical and demographic information. Supervise lollipop method of collecting a saliva sample.

Post-Visit

Collect information from participant's electronic medical record and enter into the research database.

## 5.0 INTRODUCTION

### 5.1 COVID-19 Background

Coronavirus disease 2019 (COVID-19) caused by the SARS-CoV-2 virus is most commonly spread via contact with infective respiratory droplets and aerosols produced by coughing, sneezing, talking, and singing.

Common diagnostic methods of COVID-19 infection include amplification of viral nucleic acid via polymerase chain reaction (PCR) or identification of viral antigens via rapid antigen detection kits or lateral flow assays. PCR techniques are used most frequently on nasopharyngeal (NP) swabs, but PCR performed on saliva samples can also identify infection.

### 5.2 Current Standard of Care

Current standard of care in the medical system where this study is being conducted is NP swabs for COVID-19 testing.

### 5.3 Oral Lollipop Swabs and COVID-19 PCR Testing

This study will utilize flocked swabs, referred to as “Lollipop” swabs, as a method of sample collection for PCR analysis for SARS-CoV-2. An oral lollipop swab will be obtained by placing a flocked swab into the mouth and sucking on the swab for 20 seconds as one would suck on a lollipop. Investigators have used this technique for sample collection in the diagnosis of Group A Streptococcal pharyngitis by PCR (DeMuri GP, Wald ER Detection of Group A Streptococcus in the Saliva of Children Presenting with Pharyngitis Using the cobas Liat PCR System Clinical Pediatrics May 19, 2020) and in past COVID-19 lollipop pilot studies (McBride JA, DeMuri GP, Wald ER The utility of “lollipop” swabs in the diagnosis of COVID-19 Pediatric Academic Societies Abstract May 2021). This method of sample collection to test for COVID-19 is not typically available as a standard of care outside of this study.

## 5.4 Rationale

It has been reported that the ACE2 receptor is a main host cell receptor for SARS-CoV-2 and plays a crucial role in the viral entry into human cells. There is high expression of the ACE2 receptor in epithelial cells of the oral mucosa and tongue. PCR of saliva samples have been shown to be an alternative to NP swabs.

NP swabs are cumbersome to perform, uncomfortable for the patient, require assistance from health care providers, and are not practical for large daycare and school-aged groups that may warrant repeated testing. Salivary samples can be challenging due to volume of saliva required to run the test. An oral swab, sucked on like a lollipop is a less invasive, quicker, and an easier sample to perform that may also be obtained by the individual or parent at home without a medical provider. Therefore, oral lollipop swabs may facilitate testing in adults, younger children, greater numbers of children, and when multiple longitudinal samples may be required. The oral lollipop swab will be a much more comfortable sample to obtain and will allow for the repeated and large-scale testing of populations.

In addition, PCR is a very sensitive technique that can identify persistent viral nucleic acid following acute infection. For this reason, repeat PCR tests are not recommended to determine the end point of COVID-19 isolation. Moreover, repeat COVID-19 screening via PCR is not recommended within 90 days of past infection. These persistently positive NP PCRs can lead to diagnostic and infection prevention challenges as distinguishing which tests represent true, acute, and transmissible infection versus past, non-viable, and non-transmissible virus is frequently not possible.

If the oral lollipop swab has a similar performance to the NP swab, then a new testing option, ideal for frequent testing of large cohorts of patients, especially young children, will be possible. In addition, identifying differences between NP and oral lollipop swab positivity could determine whether oral lollipop swabs have less risk of persistent, post-infectious, positivity.

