### Inclusion Criteria

1. Ability to understand and the willingness to provide verbal informed consent, if 18 years or older. If 4-17 years old, ability to understand and the willingness to provide verbal assent, plus have a parent or legal guardian present who can provide verbal informed consent.
2. Willing to comply with all study procedures and be available for the duration of the study.
3. Admitted to UW Health University Hospital or UW Health Kids American Family Children's Hospital.
4. Individuals at least 4 years of age.
5. Verified COVID-19 according to positive NP PCR test criteria.
6. Enroll within 47 hours of the diagnostic NP swab; lollipop swab collected within 48 hours of the diagnostic NP swab.
7. Either personally able or have a parent or legal guardian able to verbally answer questions in English about clinical symptoms, exposures, and other health and demographic information.

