### **12.4 Statistical Methods**

Sensitivity and specificity of the lollipop swabs will be calculated.

The primary variable is binary (positive or negative). A separate subgroup analysis of sensitivity/specificity of lollipop swabs will be calculated for asymptomatic, symptomatic (<7 days), and symptomatic (>7 days) individuals.

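### Every positive NP PCR counts as disease despite the Rationale's warning on persistent positivity; 12.4 needs a sensitivity analysis by documented recent infection

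*Combined protocol and SAP*

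**What the plan says.** Section 5.4 (Rationale) describes NP PCR as able to detect residual viral nucleic acid after acute infection. It notes that "repeat COVID-19 screening via PCR is not recommended within 90 days of past infection", and then says that "distinguishing which tests represent true, acute, and transmissible infection versus past, non-viable, and non-transmissible virus is frequently not possible". It adds that differences between the two swabs "could determine whether oral lollipop swabs have less risk of persistent, post-infectious, positivity", so a negative lollipop beside a positive NP is there a possible advantage of the new swab.

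The rest of the plan uses the NP result without that caution:

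- **Eligibility (8.1).** The disease criterion is "Verified COVID-19 according to positive NP PCR test criteria". No inclusion or exclusion criterion concerns recent infection.
- **Comparison (3.1 Synopsis).** "The results of the lollipop swab will be compared to that of the known positive NP PCR to estimate the performance" of the lollipop test. The next sentence reads "Falsely negative lollipop samples will be compared with the corresponding NP sample for cycle threshold", so a discordant pair is by definition a lollipop error.
- **Analysis (12.4).** "Sensitivity and specificity of the lollipop swabs will be calculated". The only subgroups are by symptom status and duration.
- **Data (7.1).** The items collected include "duration of symptoms, known past COVID-19 infections, known COVID-19 household contacts within 90 days", and also the NP cycle threshold. As worded, the 90 days belongs to household contacts, not to past infection.

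**The concern.** The same result, NP positive and lollipop negative, is a possible benefit in 5.4 and a false negative in 3.1 and 12.4, and nothing in the plan reconciles the two. Suppose some enrolled patients carry residual RNA from an earlier infection, and the lollipop is positive less often in them than in acute infection. The reported figure, read as sensitivity for acute infection, is then too low.

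Interpretation is what is at stake. A low value in the asymptomatic or longer-duration groups could mean that the swab misses infection or that the NP is detecting old RNA. Without a split by prior infection, the planned tables cannot help a reader separate the two. The question raised in 5.4, whether the lollipop is less prone to post-infectious positivity, also has no analysis attached to it.

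**Working it through.** **The plan's own figure.** Section 12.2 cites 88% in the pilot, anticipates about 80%, and gives N = 206 with 5% type I error and 90% power. It states no formula. A two-sided one-sample test of 0.80 against 0.88 gives

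n = [1.960 × √(0.88 × 0.12) + 1.282 × √(0.80 × 0.20)]² / 0.08² = 206.5,

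which matches. The figure is not in dispute here. It shows that the calculation appears to rest on an 8-point difference in sensitivity, a useful yardstick.

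**Model.** Let q be the share of participants whose NP is positive from a past infection, s the lollipop sensitivity in acute infection, and t the lollipop positivity in the post-infectious patients. Then

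observed sensitivity = (1 − q) × s + q × t.

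**Inputs.** s = 0.88 is the pilot figure from 12.2, used as an assumption. The pilot was itself measured against NP and may already contain persistent positives. The documents give neither q nor t. Both are assumed: q = 5%, 10%, 20% and t = 0.30, 0.50, 0.70.

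| q | t = 0.30 | t = 0.50 | t = 0.70 |
|---|---|---|---|
| 5% | 85.1% | 86.1% | 87.1% |
| 10% | 82.2% | 84.2% | 86.2% |
| 20% | 76.4% | 80.4% | 84.4% |

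For example, at q = 10% and t = 0.30: 0.90 × 0.88 + 0.10 × 0.30 = 0.792 + 0.030 = 0.822. Against 88%, the shortfall is 0.9 to 2.9 points at q = 5%, 1.8 to 5.8 at 10%, and 3.6 to 11.6 at 20%.

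**Share needed for a given fall.** Solving for q gives q = (fall) / (0.88 − t). NP sensitivity is 100% by design, because everyone enrolled is NP positive. A 50% deficit therefore means a lollipop sensitivity of 50%, a fall of 0.38 from 0.88.

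| t | q for 88% → 80% | q for 88% → 50% |
|---|---|---|
| 0 (extreme bound) | 0.08/0.88 = 9.1% | 0.38/0.88 = 43.2% |
| 0.30 | 0.08/0.58 = 13.8% | 0.38/0.58 = 65.5% |
| 0.50 | 0.08/0.38 = 21.1% | 0.38/0.38 = 100% |
| 0.70 | 0.08/0.18 = 44.4% | 0.38/0.18 > 1, impossible |

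**The case against.** The case for leaving the plan alone has real substance.

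- **The objective is performance compared with NP (6.0).** As agreement with NP, the estimate is not biased. That stands. But 12.1 and 12.4 call it sensitivity, 3.1 speaks of false negatives, and the objective is framed around diagnosing COVID-19, so it will be read as sensitivity for disease.
- **The secondary objective covers discordant results, and 3.1 plans a cycle-threshold comparison.** Relating past infection to discordance would fit that objective. It names no past-infection window or method, however, and describing discordant patients gives no sensitivity estimate without the doubtful ones. The threshold comparison is confined to false negatives and is not split by prior infection.
- **The primary hypothesis is limited to symptoms under 5 days.** This stands as substantial protection, though incomplete: a recently infected inpatient with new symptoms from another cause would still qualify.
- **Lower sensitivity is already expected.** Section 12.2 allows for a fall to about 80%, and 12.1 predicts a deficit in the asymptomatic and ≥5-day groups. Expecting a low value does not explain it.
- **Size and remedy are uncertain.** No share is documented, and a split by documented infection cannot fully resolve what 5.4 calls frequently indistinguishable. Both points stand.

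Two stronger readings are tempting. A reader might infer that persistent positives alone could produce the hypothesised 50% deficit. With t between 0.30 and 0.70 that needs about 66% of the stratum at best, and is impossible at t = 0.70; nothing in the documents supports such a share. A reader might also infer that such patients are common because screening finds many cases. Section 15.3 says only that pre-procedural and admission screening contributes to the supply of known positives.

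**Conclusion.** The gap is real and moderate. The plan names a weakness of its reference test, collects much of the data needed to examine it, and specifies no analysis that does so. Read as sensitivity for acute infection, the estimate is biased downward by an unknown amount, provided lollipop positivity is lower in post-infectious than in acute patients. The assumed inputs put the shortfall at about 1 to 12 points for shares of 5% to 20%; these figures illustrate and do not predict.

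The effect could contribute to a deficit in the asymptomatic and ≥5-day groups but is unlikely to account for a 50% deficit by itself. The primary hypothesis is least exposed. The documents also do not show that the date of past infection goes unrecorded: 10.3.1 refers to a Data Collection Sheet that is not included, and it may hold that date.

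**What to change.** Keep eligibility and the planned comparison with NP as they are. In 12.4:

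1. Describe the full-sample result as agreement with NP.
2. Add a pre-specified sensitivity analysis reporting lollipop sensitivity, overall and in each symptom stratum, with and without participants who have a documented SARS-CoV-2 infection in the 90 days before the diagnostic NP swab. Use one set of symptom boundaries; 12.1 now divides at 5 days and 12.4 at 7.
3. Show the NP cycle threshold for both sets.
4. Confirm that the Data Collection Sheet records the date of past infection, and add the field if it does not. Do this before closure, because 11.4.2 has direct identifiers destroyed then and a missing date may not be recoverable.

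The cost is at most one date field and an extra column in the sensitivity table, plus the cycle-threshold display; enrolment is unaffected. With up to 225 participants, some cells will be sparse. Unrecognised past infections will remain in the reduced set, and some participants left out may be true reinfections. For those reasons the with-and-without comparison should be reported as a partial check beside the main result, not as a corrected estimate.
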